11.0 STUDY PARAMETERS AND CALENDAR

	Screening (≤ 4 weeks prior to dosing)	Cycle 1 Day1 (+/- 3 days) ¹ *	Cycle 2+ D1 (+/- 2 or 3 days) for patients on therapy and for patients re- starting therapy ^{2*}	Patients OFF therapy: every 6 weeks (+/- 3 days) ¹³	Patients OFF therapy: Every 12 weeks (+/- 3 days) ¹³	End of Treatment (+/- 3 days) ¹⁴	Post Study follow up(+/- 3 days) ¹⁵
Informed Consent	X						
ECOG PS, Weight (screening only), Vital Signs	X	X	X	X	X	X	
History/Physic al ³	X	X	X	X	X	X	
Adverse Events		X	X	X	X	X	X
Hematology ⁴	X	X	X	X	X	X	
Chemistry ⁵	X	X	X	X	X	X	
TSH, T4, T3 ⁶	X		X		X		
Autoimmune labs ⁷	X						
Correlative Studies ⁸	X		X		X		
CPI		X	X				
Tumor Imaging ⁹	X		X		X	As clinically indicated	As clinically indicated
Brain CT or MRI ¹⁰	As clinically indicated		As clinically indicated		X	As clinically indicated	As clinically indicated
Bone Scan ¹¹	As clinically indicated		As clinically indicated		X	As clinically indicated	As clinically indicated
Biopsy ¹²				X			

*One Cycle is 14-28 days. Visit window +/- 3 days for Atezolizumab, Nivolumab, and Pembrolizumab. Visit window is +/- 2 days for Avelumab and Durvalumab.

1. Cycle 1 Day 1 Hematology, chemistry, autoimmune labs, and physical exam need not be repeated if done within 14 days

2. History, physical, AEs, Hematology, Chemistry to be done D1 (+/- 3 days) of every cycle

3. Baseline exam should be comprehensive. Subsequent physical exams can be targeted exams.

4. Hematology: CBC with differential, hemoglobin, hematocrit, platelets
5. Blood chemistry: sodium, potassium, chloride, bicarbonate, BUN, creatinine, albumin, total albumin, bicarbonate, AST, ALT, glucose, LDH (baseline only)
6. TSH, T4, T3: Screening, and on all imaging days, then as clinically indicated.
7. Autoimmune labs ANA by IFA screen, Anti-ENA, Anti-DNA DS, Rheumatoid factor, CCP antibody, ESR, CRP. These only need to be drawn if not drawn prior to initial treatment with CPI therapy.
8. Correlative studies: Correlative studies will be drawn with blood draws at biopsy, screening and prior to each imaging.
9. Tumor imaging: CT of the chest, abdomen, and pelvis (with contrast, if possible) to be performed to assess disease status at screening, and every 12 weeks from Cycle 1 Day 1. Tumor imaging should also be done whenever disease progression is suspected and as clinically indicated.
10. Brain imaging Brain CT or MRI scan to be performed as clinically indicated.
11. Bone imaging: Bone scan to be performed if clinically indicated.
12. Biopsy is recommended at any time during cycle 1 (for PR and SD patients) and within 3 weeks of any other time period at which a PD or PR is achieved in any patient (unless not feasible or unsafe per investigator discretion. Archival tissue up to 6 months prior to enrollment is acceptable in lieu of a cycle 1 biopsy
13. OFF treatment Patients will be seen every 12 weeks. The 6-week interim visit between scans will be done if clinically indicated. Labs during the 6-week interim visit should be as clinically indicated.
14. End of treatment: End of treatment visit is defined as the visit during which the patient will be removed from the study (even if not receiving drug at that visit).
15. Post- study follow up Patients will continue to be followed for at least 30 days after the last dose of CPI therapy or until new anti-cancer treatment is initiated, whichever comes first. Phone follow-up is sufficient.

12.0 MEASUREMENT OF EFFECT

Patients must have measurable disease at screening and will be evaluated for response on the basis of RECIST criteria version 1.1.⁴⁴ Tumor measurements using physical examination, spiral CT scan and/or MRI or other appropriate techniques deemed suitable by the investigator will be performed at screening within 28 days of patient registration and repeated per study calendar (Section 11.0) Scans can be done more frequently per MD discretion; these scans will be submitted on an unscheduled disease assessment.

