4.1 Inclusion Criteria

Patients must meet all the following criteria to be eligible for study enrollment.

- Men and women ≥ 18 years of age.

- Histological confirmation of urothelial carcinoma (any histology)
- Advanced or metastatic urothelial carcinoma.
- Has received at least 20 weeks on CPI therapy per standard of care (SOC) for advanced urothelial carcinoma
- Karnofsky Performance Score (KPS) $\geq 70\%$ (for more information on KPS, please see: http://www.npcrc.org/files/news/karnofsky_performance_scale.pdf)
- Willing and able to provide informed consent.
- Laboratory criteria for study entry must meet the following criteria:
 - Serum creatinine $\leq 2 \times$ ULN OR CrCl $\geq 30 \text{ mL/min}$ (measured or calculated using the Cockcroft-Gault formula).
 - Hb $\geq 8.0 \text{ g/dL}$
 - AST and ALT $\leq 3.0 \times$ ULN
 - Bilirubin $\leq 1.5 \times$ ULN (except subjects with Gilbert Syndrome, who can have total bilirubin $< 3.0 \text{ mg/dL}$)

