10.2 Tissue Correlatives

Biopsies are recommended at specific time points to investigate the genomic and immunologic markers that are associated with response or resistance to therapy. Regarding biopsy timing, a biopsy is recommended at any time during cycle 1 (for PR and SD patients) and within 3 weeks of any other time period at which a PD or PR is

achieved in any patient (unless not feasible or unsafe per investigator discretion). Fresh biopsy specimens will be sent to the Lab of [name] for nucleic acid isolation for gene expression analyses. In the event that archival tissue is only available nucleic acid will be isolated from formalin fixed tissue. A minimum of 3 unstained slides, up to 6 months prior to enrollment are allowed. Samples will be sent to the lab of [name] within 30 days of enrollment. Nucleic acid will be stored in a designated freezer at -80°C.

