14.0 STATISTICAL CONSIDERATIONS

14.1 Sample Size Justification

In this phase II study, we will enroll at least 50 patients with advanced urothelial carcinoma who are refractory to first line therapy or who are cisplatin ineligible. Patients will be treated with CPI therapy for at least 20 weeks as per standard of care (SOC), at which time those with a tumor burden reduction of 10% or greater will suspend CPI therapy. If the number of patients with tumor burden reduction of $\geq 10\%$ after 20 weeks is less than 20 patients, we will continue enrollment up to a maximum of 75 patients until the target sample size of 20 complete or partial responders has been reached. If we are not able to enroll 20 patients to the intermittent arm, after enrolling 75 patients, then we will deem the trial not feasible.

14.2 Safety considerations:

The primary safety endpoint is progression at 24 weeks post CPI suspension. Based on Keynote 045, we expect approximately 40% of patients in this group to progress within one year,⁴⁵ we would consider a progression rate of 60% or more within the first 24 weeks of CPI suspension to be unacceptable. A higher than expected rate of rapid progression would indicate CPI suspension is not safe in this patient population. Accordingly, we have incorporated continuous safety monitoring stopping rules into our design to ensure patient safety (Table 1). Specifically, we will stop

Table 1: Bayesian safety monitoring stopping rules. E.g. if we observed 4 or more PD by week 24 out of the first 6 patients, the trial will stop early.

Total number of patients	Number of patients with PD at 24 weeks
6	4-6
7 – 8	5-8
9 – 10	6-10
11 – 12	7-12
13 – 14	8-14
15 – 17	9-17
18-19	10-19

the trial early and declare CPI suspension unsafe if there is strong evidence that CPI suspension results in higher than expected rates of progression at 24 weeks. We will use Bayesian safety monitoring and stop the trial early if $\text{Prob}(\text{PD}_{24 \text{ wk}} > 0.4 \mid \text{data}) > 0.85$. We use a beta (0.4, 0.6) prior for the true rate of progression at 24 weeks, which corresponds to a prior expected progression rate of 0.4. Table 1 shows the corresponding stopping boundaries. If a patient progressed or died of disease, or lost to follow-up before 12 weeks, then the patient will be considered failure. Table 2 summarizes the operating characteristics.

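### Sections 4.1 and 12.0 together shut out patients with no measurable disease at screening, including those already in complete response, although 14.1 counts complete responders toward the 20

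*Combined protocol and SAP*

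**What the plan says.** All references are to the combined protocol and SAP.

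- **4.1** lists, among criteria that must all be met for enrollment, "Has received at least 20 weeks on CPI therapy per standard of care (SOC) for advanced urothelial carcinoma". Measurable disease is not on that list.
- **12.0** adds the requirement separately: "Patients must have measurable disease at screening". The tumor measurements "will be performed at screening within 28 days of patient registration".
- **14.1** keeps enrolling, up to 75 patients, "until the target sample size of 20 complete or partial responders has been reached".
- **14.3** takes as its primary efficacy endpoint a response maintained 36 weeks after suspension, estimated as a proportion with an exact 95% interval.

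On the order of events the text points both ways.

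- Screening before CPI: 14.1 writes in the future tense, "Patients will be treated with CPI therapy for at least 20 weeks as per standard of care (SOC", and the first calendar column in 11.0 is headed "Screening (≤ 4 weeks prior to dosing".
- Screening after CPI has begun: besides 4.1, calendar note 7 says of the autoimmune labs "These only need to be drawn if not drawn prior to initial treatment with CPI therapy". Section 10.2 says "a biopsy is recommended at any time during cycle 1 (for PR and SD patients", which presumes a response category by cycle 1.

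**The concern.** A measurable-disease rule normally applies to the scan from which shrinkage will be measured. Here, on the order set by 4.1, it applies to a scan taken well into treatment. It therefore removes patients whose tumors have responded so fully that nothing measurable is left.

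Those patients are part of the population that 14.1 intends to count. If 12.0 is enforced, the 36-week proportion describes patients who still had measurable disease at entry, and says nothing about those who had already cleared it. If a site enrolls them anyway, each is an eligibility deviation. A site that works from the 4.1 list alone and a site that also applies 12.0 would admit different patients. Candidates are also lost from a trial that declares itself infeasible if 75 patients do not yield 20, that is 20/75 = 27%.

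**Working it through.** **1. The plan's own figures.** The largest half-width of an exact (Clopper-Pearson) 95% interval at n = 20 is 0.228, which agrees with the stated 0.23. Exact enumeration of the Table 1 boundaries gives early-stopping probabilities of 0.120, 0.343, 0.646 and 0.883 at true progression rates of 0.3, 0.4, 0.5 and 0.6. Table 2 prints 0.12, 0.34, 0.65 and 0.88. None of these depends on the point below.

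**2. Timing under 4.1.** Inputs: at least 20 weeks of CPI before enrollment (4.1), and a screening scan within 28 days, or 4 weeks, of registration (12.0). Taking enrollment and registration as the same date, the earliest screening scan is 20 − 4 = 16 weeks after the first CPI dose. Section 1.3 puts the usual time to response at 1.4 to 2.85 months, and 2.85 × 52/12 = 12.4 weeks. The scan therefore falls after responses have typically begun. That figure concerns first response, not complete response, so it shows the order of events and not how many patients are affected.

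**3. Who passes on that order.**

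| Status at the screening scan | 4.1 | 12.0 | Counted by 14.1? |
|---|---|---|---|
| Complete response, or a response with no lesion still measurable | met | fails | would be, but cannot enter |
| Measurable disease, at least 10% reduction | met | met | yes |
| Measurable disease, less than 10% reduction so far | met | met | yes, if a response follows on study |

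The third row matters. Section 3.3 keeps such patients on CPI, and 3.1 note 3 and 6.4 item 6 allow consecutive scans before removal. One who later reaches complete response is counted.

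**4. Timing under 14.1 and the calendar heading.** If screening precedes the first CPI dose, CPI received at screening is 0 weeks, below the 20 that 4.1 requires. No patient is then eligible. Rule 12.0 would be harmless on this order, but 4.1 could not be met.

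**5. The baseline for the 10% reduction.** On the 4.1 order, the screening scan is at least 16 weeks into treatment and cannot be the starting point for the reduction that qualifies a patient. An earlier scan is needed. No section that could be read requires one or says which it is.

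**6. Off-therapy progression (secondary).** The 3.1 footnote compares imaging with scans, in the plural, taken before the intermittent phase. Suppose the sum is 80 at the last scan before suspension, 60 at week 12 and 80 at week 24. Growth is 0% from the last scan before suspension but 80/60 − 1 = 33% from the smallest sum. The choice of reference decides whether this is progression.

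**The case against.** The strongest reply is that the protocol means to screen before CPI, so that 12.0 is an ordinary pre-treatment rule. There is more support for this than 14.1 and the calendar heading alone. Section 3.1 says patients will receive CPI at standard dosing, the exclusions in 4.2 are timed to a first dose of study drug, and the calendar places CPI at Cycle 1 Day 1 and counts imaging from that day. Section 2.3 wants blood at the start of treatment. The 10.2 biopsy sentence is also weak evidence for the other order, since calendar note 12 accepts archival tissue up to 6 months old. All of this stands as evidence of intent. It does not rescue the text, because 4.1 is the operative eligibility list and nobody screened before CPI can satisfy it.

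Three stronger readings are tempting, and the documents do not support them.

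- *All complete responders are excluded.* They are not. Only those with no measurable disease at the screening scan are, and only if 4.1 timing is followed.
- *The loss can be counted.* Dividing complete-response rates by overall response rates in Section 1.2 gives 2/19.6 = 10% (nivolumab phase II), 8.1/28.9 = 28% (pembrolizumab first line) and 9/23 = 39% (atezolizumab cohort A), or about 2 to 8 of 20. But these are responses over whole trials, not status at this screening scan.
- *Off-therapy progression is read against the pre-CPI scan, so the Table 1 rule is weakened.* The footnote permits that reading but does not direct it. The synopsis, 3.3 and 12.0 all tie progression to RECIST. Any effect on stopping would need the share of progressions missed, which the documents do not give.

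**Conclusion.** The conflict is real and follows from the text. With 4.1 and 12.0 both applied, patients without measurable disease at the screening scan, including those already in complete response, cannot enter a trial whose target in 14.1 includes complete responders. With the opposite timing, 4.1 itself cannot be met. One stated rule is wrong on either reading.

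The consequence is for who makes up the 20 and how the 36-week proportion can be described. The stated precision, the sample size and Tables 1 and 2 are unaffected, and no number of excluded patients is claimed. The conclusion assumes that no exemption or clarification sits in the 3.1 schema or in the registration section (5.0), neither of which could be read. The off-therapy reference scan is an ambiguity that merits an optional clarification, no more.

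**What to change.** **12.0.** Replace the screening requirement with, for example: *Patients must have had measurable disease on the last routine-care scan before the first CPI dose; measurable disease at screening is not required. The 10% reduction is the change in the sum of target lesions from that scan to the qualifying scan.*

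**14.1 and the calendar heading.** Align both with 4.1: in 14.1, state that patients will have completed at least 20 weeks of CPI before enrollment; in 11.0, define screening as within 4 weeks before registration.

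**3.1 footnote (optional).** State that off-therapy progression is an increase of at least 20% (RECIST 1.1) from the smallest sum recorded at or after the last scan before suspension, or a new lesion, or reappearance of disease after complete response. The last clause is useful once complete responders can enter, because a percentage increase from a sum of zero is undefined. Fixing the last scan before suspension as the only reference would not be enough: it would miss the 80, 60, 80 regrowth shown above.

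**Cost.** These are wording changes. Routine-care scans from before CPI must be retrieved and their target lesions measured, and patients without a measurable one cannot enter. The documents do not say how many that would be.

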13.0 DATA REPORTING / REGULATORY CONSIDERATIONS

13.1 Data Reporting

The Forte™ EDC and OnCore® databases will be utilized, as required by the Case Comprehensive Cancer Center and Cleveland Clinic, to provide data collection for both accrual entry and trial data management. Forte™ EDC and OnCore® are Clinical Trials Management Systems housed on secure servers. Access to data through Forte™ EDC and OnCore® is restricted by user accounts and assigned roles. Once logged into the Forte™

EDC or OnCore® system with a user ID and password, Forte™ EDC and OnCore® define roles for each user which limits access to appropriate data. User information and password can be obtained by contacting the OnCore® Administrator at [contact] for OnCore® access, and [contact] for Forte™ EDC access.

Forte™ EDC is designed with the capability for study setup, activation, tracking, reporting, data monitoring and review, and eligibility verification. When properly utilized, Forte™ EDC is 21 CFR 11 compliant. This study will utilize electronic Case Report Form completion in the Forte™ EDC database. A calendar of events and required forms are available in Forte™ EDC.

13.2 Regulatory Considerations

The study will be conducted in compliance with ICH guidelines and with all applicable federal (including 21 CFR parts 56 & 50), state or local laws.

13.2.1 Written Informed consent

Provision of written informed consent must be obtained prior to any study-related procedures. The Principal Investigator will ensure that the subject is given full and adequate oral and written information about the nature, purpose, possible risks and benefits of the study as well as the subject's financial responsibility. Subjects must also be notified that they are free to discontinue from the study at any time. The subject should be given the opportunity to ask questions and be allowed time to consider the information provided.

The original, signed written Informed Consent Form must be kept with the Research Chart in conformance with the institution's standard operating procedures. A copy of the signed written Informed Consent Form must be given to the subject. Additionally, documentation of the consenting process should be located in the research chart.

13.2.2 Subject Data Protection

In accordance with the Health Information Portability and Accountability Act (HIPAA), a subject must sign an authorization to release medical information to the sponsor and/or allow the sponsor, a regulatory authority, or Institutional Review Board access to subject's medical information that includes all hospital records relevant to the study, including subjects' medical history

13.2.3 Retention of records

The Principal Investigator of the Case Comprehensive Cancer Center supervises the retention of all documentation of adverse events, records of study drug receipt and dispensation, and all IRB correspondence for as long as needed to comply with local,

national and international regulations. No records will be destroyed until the Principal Investigator confirms destruction is permitted.

13.2.4 Audits and inspections

Authorized representatives of the sponsor, a regulatory authority, an Independent Ethics Committee (IEC) or an Institutional Review Board (IRB) may visit the site to perform audits or inspections, including source data verification. The purpose of an audit or inspection is to systematically and independently examine all study-related activities and documents to determine whether these activities were conducted, and data were recorded, analyzed, and accurately reported according to the protocol, Good Clinical Practice (GCP), guidelines of the International Conference on Harmonization (ICH), and any applicable regulatory requirements. For multi-center studies, participating sites must inform the sponsor-investigator of pending audits.

14.0 STATISTICAL CONSIDERATIONS

14.1 Sample Size Justification

In this phase II study, we will enroll at least 50 patients with advanced urothelial carcinoma who are refractory to first line therapy or who are cisplatin ineligible. Patients will be treated with CPI therapy for at least 20 weeks as per standard of care (SOC), at which time those with a tumor burden reduction of 10% or greater will suspend CPI therapy. If the number of patients with tumor burden reduction of $\geq 10\%$ after 20 weeks is less than 20 patients, we will continue enrollment up to a maximum of 75 patients until the target sample size of 20 complete or partial responders has been reached. If we are not able to enroll 20 patients to the intermittent arm, after enrolling 75 patients, then we will deem the trial not feasible.

14.2 Safety considerations:

The primary safety endpoint is progression at 24 weeks post CPI suspension. Based on Keynote 045, we expect approximately 40% of patients in this group to progress within one year,⁴⁵ we would consider a progression rate of 60% or more within the first 24 weeks of CPI suspension to be unacceptable. A higher than expected rate of rapid progression would indicate CPI suspension is not safe in this patient population. Accordingly, we have incorporated continuous safety monitoring stopping rules into our design to ensure patient safety (Table 1). Specifically, we will stop

Table 1: Bayesian safety monitoring stopping rules. E.g. if we observed 4 or more PD by week 24 out of the first 6 patients, the trial will stop early.

Total number of patients	Number of patients with PD at 24 weeks
6	4-6
7 – 8	5-8
9 – 10	6-10
11 – 12	7-12
13 – 14	8-14
15 – 17	9-17
18-19	10-19

the trial early and declare CPI suspension unsafe if there is strong evidence that CPI suspension results in higher than expected rates of progression at 24 weeks. We will use Bayesian safety monitoring and stop the trial early if $\text{Prob}(\text{PD}_{24 \text{ wk}} > 0.4 \mid \text{data}) > 0.85$. We use a beta (0.4, 0.6) prior for the true rate of progression at 24 weeks, which corresponds to a prior expected progression rate of 0.4. Table 1 shows the corresponding stopping boundaries. If a patient progressed or died of disease, or lost to follow-up before 12 weeks, then the patient will be considered failure. Table 2 summarizes the operating characteristics.

Table 2. Summary of operating characteristics based on 10,000 simulations using monitoring rules specified in table 1. If the true PD rate at 24 weeks is 60%, the early stopping probability is 0.88.

Scenario	True PD rate at 24 weeks	Pr(Early Stoppng)	Average Sample Size	Average Number of PD Observed by Week 24
1	0.3	0.12	18.6	5.6
2	0.4	0.34	16.3	6.5
3	0.5	0.65	12.9	6.5
4	0.6	0.88	9.7	5.8

14.3 Efficacy:

Our primary efficacy endpoint is sustaining a response at 36 weeks following CPI suspension, and our primary objective is to estimate the proportion of patients able to sustain a response. We will estimate this proportion and construct an exact binomial 95% CI. With 20 patients, the half-width of the 95% CI won't exceed 0.23.

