3.3 Expected Duration of Treatment and Subject Participation

Each study cycle consists of 14-28 days, depending on which CPI is chosen. CPI of choice will be administered on day 1.

All patients who do not meet criteria for the CPI intermittent phase of the study will be treated until unacceptable toxicity or RECIST-defined PD. Patients with RECIST-defined PD may continue CPI therapy at the discretion of the treating MD. These patients will continue with normal imaging every 12 weeks. In cases where a patient is continued on therapy after PD and develops subsequent PD ($\geq 20\%$ increase in sum of target lesions compared to the initial PD tumor measurements, the patient will come off study).

Patients who meet criteria for the intermittent phase (i.e., have $\geq 10\%$ tumor burden reduction) will not receive CPI therapy. Imaging will continue per protocol (every 12 weeks from the initial date they stopped CPI therapy). Patients who have RECIST defined PD on the intermittent phase should reinitiate CPI therapy. Patients who have a subsequent decrease in tumor burden $\geq 10\%$ can then restart CPI therapy as per protocol. (refer to schema in Section 3.1).

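### Section 14.2 defines a failure by week 12, but the safety endpoint, the stopping criterion and Tables 1 and 2 all run to week 24

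*Combined protocol and SAP*

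**What the plan says.** Section 14.2 of the combined protocol and SAP sets the window at the start: "The primary safety endpoint is progression at 24 weeks post CPI suspension". The unacceptable level has the same window: "we would consider a progression rate of 60% or more within the first 24 weeks of CPI suspension to be unacceptable". The trial stops if the posterior probability that the 24-week PD rate exceeds 0.4 is above 0.85, with a beta(0.4, 0.6) prior on that rate. The example with Table 1 stops the trial "if we observed 4 or more PD by week 24 out of the first 6 patients". Table 2 is indexed by the same rate: "If the true PD rate at 24 weeks is 60%, the early stopping probability is 0.88".

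Between the references to Table 1 and Table 2 stands the only sentence that classifies patients: "If a patient progressed or died of disease, or lost to follow-up before 12 weeks, then the patient will be considered failure".

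Section 3.3 schedules off-therapy imaging "every 12 weeks from the initial date they stopped CPI therapy", which puts scheduled scans at weeks 12 and 24. The study calendar in Section 11.0 gives a window of ±3 days and adds, in note 9, "Tumor imaging should also be done whenever disease progression is suspected and as clinically indicated".

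**The concern.** The sentence can be read in two ways, and neither gives a complete counting rule for Table 1.

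- **Reading 1.** The 12-week limit covers progression, death and loss alike. A PD at week 20 is then not a failure, although Table 1 counts PD to week 24.
- **Reading 2.** The limit covers only loss to follow-up. PD counting to week 24 is intact, but a patient lost in weeks 12 to 24 is not made a failure, and nothing says whether that patient is a non-failure or leaves the denominator.

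Table 1 is the trial's only statistical stopping rule for progression after suspension. It is applied continuously and its boundaries are small counts, so a single classification can decide whether the trial stops. If the rule is unclear, that classification may be settled once its consequence is already known. Table 2 describes the rule's behaviour only if failures are counted to week 24.

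**Working it through.** **Inputs from the documents.** Beta(0.4, 0.6) prior; threshold 0.4; posterior cut-off 0.85; looks at n = 6 to 19 (Table 1); maximum of 20 patients in the intermittent arm (synopsis and Section 3.2). The documents give neither the timing of progression within the 24 weeks nor a loss rate. Both are assumed below and shown as ranges.

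**1. Table 1.** After r failures in n patients the posterior is Beta(0.4 + r, 0.6 + n − r). The boundary is the smallest r with P(rate > 0.4) > 0.85. All 14 boundaries for n = 6 to 19 reproduce.

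**2. Table 2.** An exact recursion over binomial paths, checking the boundary after each patient from 6 to 19, gives:

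| True 24-week PD rate | Stopping, recomputed | Stopping, Table 2 | Mean N, recomputed | Mean N, Table 2 |
|---|---|---|---|---|
| 0.3 | 0.120 | 0.12 | 18.6 | 18.6 |
| 0.4 | 0.343 | 0.34 | 16.3 | 16.3 |
| 0.5 | 0.646 | 0.65 | 12.9 | 12.9 |
| 0.6 | 0.883 | 0.88 | 9.7 | 9.7 |

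Both tables are therefore right for a 24-week count.

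**3. One patient, no assumption about hazard.** The first 6 patients include 3 with PD and 1 lost at week 16.

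- Loss counted as a failure: 4/6, Beta(4.4, 2.6), posterior 0.893 > 0.85, stop.
- Loss counted as a non-failure: 3/6, Beta(3.4, 3.6), posterior 0.668, continue.
- Loss removed: 3/5, Beta(3.4, 2.6), posterior 0.796. Table 1 has no row for 5 patients, so the trial continues.

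**4. Reading 1 at a true 24-week rate of 0.60.** The same boundaries are applied to the 12-week rate.

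- Constant hazard (assumed): 1 − √(1 − 0.60) = 0.368; stopping 0.257; mean N 17.2 instead of 9.7.
- 50%, 70% or 90% of progressions by week 12 (assumed): 0.60 × 0.5, 0.7 or 0.9 = 0.30, 0.42 or 0.54; stopping 0.120, 0.401 or 0.756.

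**5. Reading 2.** Let L be the share of patients whose 24-week status is lost, taken as independent of progression (assumed). For a true rate p, the counted rate is p(1 − L) if losses are non-failures and p + L(1 − p) if they are failures. If losses are removed and replaced it stays at p.

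| p | L | Stopping, non-failure | Stopping, failure | Stopping, replaced |
|---|---|---|---|---|
| 0.4 | 5% | 0.288 (rate 0.38) | 0.432 (rate 0.43) | 0.343 |
| 0.4 | 10% | 0.238 (rate 0.36) | 0.524 (rate 0.46) | 0.343 |
| 0.6 | 5% | 0.826 (rate 0.57) | 0.913 (rate 0.62) | 0.883 |
| 0.6 | 10% | 0.756 (rate 0.54) | 0.937 (rate 0.64) | 0.883 |

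**The case against.** Reading 2 is the more natural one. Every other statement in Section 14.2 says 24 weeks, and a team using Table 1 as labelled would count a PD at week 20. The calendar points the same way: a patient lost before week 12 normally has no scheduled scan after suspension, so treating that patient as a failure is coherent. Taken strictly, Reading 1 would even leave out PD found on the week-12 scan. The fall to 0.26 needs both Reading 1 and an assumed hazard. The six-patient example is set one event below the boundary; it shows that a loss can matter, not how often it would. Counting every loss as a failure is also a missing-data choice, since replacing lost patients would keep 0.34 and 0.88.

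Much of this stands. The Reading 1 figures are conditional, and 0.88 holds with complete follow-up. But Reading 2 still leaves losses in weeks 12 to 24 without a rule, and Section 6.4 allows exits such as withdrawal of consent. Replacement keeps the operating characteristics only if loss is unrelated to progression, and it departs from the plan's own treatment of early losses. Two smaller points are fair. Deaths not due to disease have no stated classification, and note 9 of Section 11.0 also anchors imaging at Cycle 1 Day 1, which differs from Section 3.3. Neither changes the main point.

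**Conclusion.** The concern holds. The failure sentence does not match the 24-week endpoint it is meant to serve, and no section explains a 12-week limit. Tables 1 and 2 are correct and can stay.

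That one classification can switch the decision (0.893 against 0.668) needs no assumption about hazard. How far the stopping probability moves at a true rate of 60% does depend on assumptions. It is 0.12 to 0.76, against 0.88, if only events by week 12 are counted and 50% to 90% of progressions fall by then. It is 0.83 or 0.76 if 5% or 10% of PD events are missed through later loss and entered as non-failures. This should be corrected, because the rule protects patients taken off therapy and needs a clear event definition before data accrue.

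**What to change.** Replace the sentence in Section 14.2 with a 24-week rule, for example: *A patient is a failure for Table 1 if PD or death from disease occurs by week 24, or if follow-up ends before a week-24 assessment (scheduled scan ±3 days) shows no PD.* This extends the plan's own treatment of early losses to its own endpoint window. Relabel the rate in Table 2 as the 24-week failure rate. Also state how deaths from other causes are classified; counting them as failures is optional and would change the endpoint.

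The cost is a one-sentence amendment and a column label, with the boundaries unchanged. The statistical price is that losses unrelated to progression count against suspension. At a 40% PD rate, 3 or 5 added percentage points of such losses (failure rate 0.43 or 0.45) raise stopping from 0.34 to 0.43 or 0.49; a 10% independent loss (0.46) gives 0.52. At 60% PD, 2 added points (0.62) raise it from 0.88 to 0.91, and a 10% loss (0.64) gives 0.94. If the sponsor prefers to replace lost patients, that rule should be written down instead, with its assumption that loss is unrelated to progression.
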